### Muscle Glycogen

Approximately 20 mg of muscle will be dehydrated in a freeze dryer. Samples will then be ground to powder and visible connective tissue will be removed. Powdered muscle will be placed in 500  $\mu$ l 2 N HCl. Samples will then be placed in an incubator for 120 min at 100°C. Following incubation samples will be neutralized with 1500  $\mu$ l 0.67 N NaOH and glycogen will be quantified by a fluorometric assay (Sigma-Aldrich, St. Louis, MO, USA).

### Immunofluorescence staining, microscopy, and image analysis

To determine GLUT4 translocation to the cellular membrane in response to exercise and carbohydrate intake immediately after sample collection by muscle biopsy, excess blood and any visible collagen and/or fat will be removed and muscle will be embedded in Tissue Tek Optimum Cutting Temperature (OCT) compound (VWR International, Leicester, UK) and frozen in liquid nitrogen. Frozen muscle biopsy samples will be cryosectioned to a thickness of 5  $\mu$ m onto uncoated glass microscope slides (VWR International). Sections will be fixed in 75% acetone and 25% ethanol solution for 5 min, then washed 3 times for 5 min in phosphate-buffered saline (PBS). A previously validated (31, 32) GLUT4 and dystrophin primary antibody (Abcam, Cambridge, UK) will be applied to muscle sections at a 1:200 and 1:400, respectively, dilution in 5% normal goat serum (Invitrogen, Carlsbad, CA, USA) for 2-hr at room temperature. Dystrophin staining will allow for visualization of the plasma membrane to determine GLUT4 location. Following primary antibody incubation, sections will be washed 3 times for 5 min in PBS and then incubated in 1:200 dilutions of secondary antibodies AlexaFluor 488-conjugated goat anti-rabbit IgG (Invitrogen; GLUT4) and AlexaFluor 594-conjugated goat anti-mouse IgG2b (Invitrogen; Dystrophin) for 30 min at room temperature. Sections will then be washed 3 times for 5 min in PBS and glass coverslips will be mounted with 20  $\mu$ l mowiol mounting medium [6 g glycerol (Sigma-Aldrich), 2.4 g mowiol 4–88 (Sigma-Aldrich) and 0.026 g 1,4-Diazabicyclo[2.2.2]octane (DABCO) (Sigma-Aldrich) dissolved in 18 mL 0.2 M Tris-buffer (pH 8.5) (Sigma-Aldrich)]. Images will be captured using a Nikon TI-U inverted microscope equipped with a Retiga 2000R camera and NIS-Elements

1 image analysis software (Nikon, Tokyo, Japan) to determine colocalization of GLUT4 and dystrophin.  
2 Quantitation of GLUT4 in the plasma membrane (dystrophin-stained region) will be performed using  
3 Imaging software.  
4

#### 5 mRNA and microRNA Expression

6 To understand potential molecular regulation of changes in substrate metabolism during exercise at SL  
7 and HA this study will examine alterations in expression profiles of mRNA and microRNA that are  
8 associated with substrate metabolism. Total RNA will be isolated from approximately 25 mg of muscle  
9 using a mirVana™ miRNA isolation kit (Invitrogen, Carlsbad, CA, USA). Quantity and quality of RNA  
10 will be assessed using a Nanodrop ND-1000 spectrophotometer (Nanodrop, Wilmington, DE, USA).  
11 Equal amounts of total RNA will be synthesized into cDNA for analysis of mRNA (High-Capacity cDNA  
12 RT Kit, Applied Biosystems, Foster City, CA, USA) and a TaqMan® microRNA RT kit (Applied  
13 Biosystems). Individual primers will be used to determine the mRNA expression of known intracellular  
14 targets regulating substrate metabolism, through glycolysis, TCA cycle, fatty acid oxidation, and  
15 glucose uptake. Individual primers will be used to determine microRNA expression of microRNA that  
16 have been reported to impact metabolism within the muscle.  
17

18 Circulating miRNA will be extracted from serum using previously published methodologies (33). Due to  
19 the small amount of RNA in the serum, 3.5 µL of a Spike-In Control (C. elegans miR-39; Qiagen) A pre-  
20 amplification step will be performed after reverse transcription to increase cDNA template using a  
21 primer pool of 20 X Taqman® Small RNA Assays (Applied Biosystems) for miRNA of interest at 0.05X  
22 concentration in 1X TE buffer. All serum miRNA will be normalized to the geometric of external (Spike-  
23 In Control C. elegans miR-39) and internal controls to allow for both technical and inter-individual  
24 normalization (34). Geometric mean of controls will be used to correct for possible outlying values and  
25 abundance differences between the different controls (35).  
26

27 All reverse transcription for mRNA and miRNA, and pre-amplification of serum miRNA will be  
28 conducted in a T100™ Thermal Cycler (Bio-Rad, Hercules, CA). A StepOnePlus™ real-time PCR  
29 system (Applied Biosystems) will be used to perform all mRNA and miRNA analysis. Fold changes will  
30 be calculated using the  $\Delta\Delta$  cycle threshold ( $\Delta\Delta C_T$ ) method as described below in statistical analysis  
31 section.  
32

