#### 43 44 Altitude Chamber

45 To simulate ascension to high altitude volunteers will perform one arm of this crossover study in a  
46 hypobaric (altitude) chamber under temperate ( $20^\circ\text{C}$ , 30-50% rh;  $12\text{-}16^\circ\text{C}$  Wet Globe Bulb  
47 Temperature (WGBT)) ambient conditions. The chamber will reduce barometric pressure, and thus  
48 ambient oxygen pressure, to a value similar to that at the summit of Pike Peak, CO (4,300 m).  
49 Volunteers will be exposed to hypobaric/hypoxic conditions for 5-hrs before beginning steady-state  
50 exercise to mimic our past investigations. Total time in the chamber on the protocol day will be ~7-8-  
51 hrs. All activities within the altitude chamber will be monitored by trained study staff. The chamber is  
52 on a regular maintenance schedule and chamber performance is documented each test day.

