**Exercise Protocol Day**

Two catheters will be placed into the lower arm (one in each arm). One arm will be used for infusion of 6,6-[H2] glucose tracer and the other will be used for blood sampling under resting and exercise conditions. Following an initial blood and breath sample collection to determine background enrichments, a primed, continuous infusion of 6,6-[H2] glucose will begin (prime, 82.2 μmol·kg; continuous rate, 0.78 μmol·kg·min, **Figure 4**) (24, 25). Volunteers will complete 80-min of steady-state exercise on a treadmill at 55 ± 5% of their VO2peak determined at HA, performing the same absolute work under both study conditions. V̇O2, V̇CO2, HR, and SaO2 will be measured at approximately 320, 330, 340, 360, 380, and 395 min. During exercise volunteers will consume a CHO beverage at 1.8 g·min to examine the impact of altitude exposure on exogenous carbohydrate oxidation efficiency. Drinks will contain 145 g glucose, with a total volume of 1450 mL. The drink will be consumed in four boluses throughout the 80-min of steady-state exercise (320, 340, 360, and 380-min). The first bolus will be 550 mL, with the remaining three being 300 mL. The CHO beverage consumed during exercise will be enriched with 200 mg U-C-glucose (Cambridge Isotope Laboratory, Andover, MA, USA) to increase the isotopic enrichment well above natural levels and optimize the measurement of exogenous carbohydrate oxidation. Before exercise, during the HA phase, volunteers will be exposed to hypobaric hypoxic conditions for 5-hrs to mimic our previous investigation. Muscle samples will be obtained using percutaneous muscle biopsy, taken from the vastus lateralis using a 5-mm Bergstrom needle with manual suction while the volunteer is under local anesthesia (1% lidocaine) according to the approved USARIEM SOP (26, 27). Muscle samples will be collected before (300 min) and immediately (420 min) after 80-min of steady state exercise during both the SL and HA protocol study days. The two muscle biopsy collections will occur from one incision each protocol day. Following a minimum 7-d washout period, volunteers will return to the laboratory to complete the second arm of the investigation. A total of four muscle biopsies will be conducted per volunteer, two per protocol day, with one incision made on each leg.

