### 39 **B5.8.2 Data analysis**

40  
41 Statistical analyses will be conducted using either SPSS (IBM Corp. Armonk, NY), SAS 9.3 (SAS  
42 Institute Inc., Carey, NC), or equivalent. Common descriptive statistics will be used to describe  
43 volunteer characteristics. Shapiro-Wilk tests will be used to determine normality of data. Paired t-  
44 test will be performed to determine main effects of phase (SL versus HA) for glucose turnover and  
45 glucose oxidation. Mixed model repeated measures ANOVA will be performed to determine main  
46 effects of time (baseline versus post-exercise), phase (SL versus HA) and time-by-phase  
47 interactions for glucose and insulin concentrations, GLUT4 translocation, glycogen, mRNA and  
48 microRNA, Western blots and enzyme activity. If interactions are significant, appropriate post-  
49 hoc correction will be used to examine these relationships. Correlation coefficients and multiple  
50 regression analysis will be used to evaluate relationships between study outcome measures. The  
51 alpha level will be adjusted for multiple comparisons, with the level for statistical significance set  
52 at  $P < 0.05$ .  
53

---

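### The plan does not say on which scale, or against which calibrator, mRNA and microRNA are modelled; fold changes against a common sea-level calibrator can produce a time-by-phase interaction that is absent on the CT scale

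*Combined protocol and SAP*

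**What the plan says.** The mRNA and microRNA part of B5.4 states that the real-time PCR system "will be used to perform all mRNA and miRNA analysis. Fold changes will" be calculated with the delta-delta-CT method, "method as described below in statistical analysis" section. Fold change is the only RNA expression measure the plan defines.

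The statistical section, B5.8.2, specifies a mixed-model repeated-measures ANOVA for main "effects of time (baseline versus post-exercise), phase (SL versus HA) and time-by-phase" "interactions for glucose and insulin concentrations, GLUT4 translocation, glycogen, mRNA and" microRNA, among other outcomes. A significant interaction leads to post-hoc comparisons. The section does not mention delta-delta-CT, delta-CT, a calibrator (reference) sample or a log scale. Its only distributional step is a Shapiro-Wilk test, and no consequence of failing it is given.

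For muscle RNA the two-by-two layout comes from the Exercise Protocol Day text in B5.3: "Muscle samples will be collected before (300 min) and immediately (420 min) after 80-min of steady state exercise during both the SL and HA" protocol days. At altitude the first of these biopsies comes late in a long hypoxic exposure: "Volunteers will be exposed to hypobaric/hypoxic conditions for 5-hrs before beginning steady-state" exercise.

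**The concern.** PCR effects act on the CT scale, which is a log2 scale. Effects that add there multiply on the fold scale, so whether exercise and altitude interact can depend on the scale chosen. A linear model fitted to fold changes asks whether effects add on a scale where, with no biological interaction, they would be expected to multiply.

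Both main effects are plausible in this design. The pre-exercise biopsy at altitude follows hours of hypoxia, and the second biopsy follows 80 minutes of exercise.

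The interaction is also the term the plan acts on. It carries the claim that altitude changes the muscle's molecular response to exercise, which belongs to the mechanistic part of the objective in B4. On the wrong scale that claim could be made when the fold response to exercise is the same in both phases, or missed when it differs.

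**Working it through.** The plan gives no figure for the RNA analysis, so there is none to reproduce.

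**Inputs from the documents.** 10 volunteers in a crossover (B5.8.1); two times by two phases (B5.3, B5.8.2); alpha 0.05 (B5.8.2).

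**Assumptions, not in the documents.** Two-sided tests, no multiplicity adjustment, between-person SD 0.5 cycles, within-person SD 0.3, 0.5 or 0.8 cycles, and the effect sizes shown below.

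**Step 1: algebra with a common calibrator.** Let exercise multiply expression by a and altitude by b, with no interaction on the CT scale. Relative to sea-level pre-exercise, the cells are 1 (SL pre), a (SL post), b (HA pre) and ab (HA post). The fold-scale interaction contrast is

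ab − b − a + 1 = (a − 1)(b − 1).

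- a = 2, b = 2: 4 − 2 − 2 + 1 = 1.0
- a = 2, b = 1.5: 3 − 1.5 − 2 + 1 = 0.5
- a = 1.5, b = 1.5: 2.25 − 1.5 − 1.5 + 1 = 0.25
- a = 1 or b = 1: 0

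On the log2 scale the contrast is log2(ab) − log2(b) − log2(a) + 0 = 0 in every case.

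**Step 2: how often the test rejects.** 20,000 simulated trials per setting. The within-person interaction contrast is tested with a one-sample t on 9 degrees of freedom, which is the two-by-two repeated-measures interaction test. The calibrator is each volunteer's own sea-level pre-exercise sample.

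| Exercise, altitude | SD 0.3 | SD 0.5 | SD 0.8 |
|---|---|---|---|
| x1.5, x1.5 | 16% | 7% | 4% |
| x2, x1.5 | 35% | 13% | 5% |
| x2, x2 | 75% | 29% | 9% |
| x3, x2 | 97% | 56% | 18% |
| only one effect present | 4–5% | 4–5% | 4–5% |
| delta-CT, any setting | about 5% | about 5% | about 5% |

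A group-mean sea-level calibrator gives similar rates: 73%, 31% and 13% for x2 with x2.

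**Step 3: a separate calibrator for each phase.** If each phase is referred to its own pre-exercise sample, the cells are 1, a, 1, a. The interaction is a − 1 − a + 1 = 0, and the simulated rate is 4–5% even with two large effects.

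This choice has a cost. Write the post-exercise values as a_SL and a_HA. The phase contrast is (1 + a_HA)/2 − (1 + a_SL)/2 = (a_HA − a_SL)/2. The interaction contrast is a_HA − a_SL. These are the same test, and the altitude effect at rest has been divided out. B5.8.2 promises a phase effect and an interaction as separate results, so a common calibrator fits the stated model better.

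**Step 4: masking.** Take exercise x2, altitude x0.67 and a true interaction of +0.6 cycles (altitude strengthens the exercise response by 2^0.6 = 1.52). The HA post cell is 2 × 0.67 × 1.52 = 2.02, so the fold-scale contrast is 2.02 − 0.67 − 2 + 1 = 0.35. The scale term (2 − 1)(0.67 − 1) = −0.33 cancels about half of the 0.69 that the true interaction contributes. Simulated power is about 32% (SD 0.3) and 13% (SD 0.5) on the fold scale, against 80% and 40% on delta-CT. An interaction of the opposite sign would be exaggerated instead.

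**The case against.** The strongest reply is that this is a missing specification rather than a wrong choice. B5.4 says fold changes are calculated, and B5.8.2 lists mRNA and microRNA as outcomes. No sentence says that the fold change itself, rather than delta-CT or log2 fold, is the ANOVA response. A team that models delta-CT and reports fold changes would comply with both sections. This stands. That fold changes enter the model is the plain reading, because no other RNA measure is defined, but it remains an inference.

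A reader might also infer that any pair of real exercise and altitude effects will yield false interactions. The documents do not support that. The calibrator is not named, and with a separate one for each phase the artefact disappears. Even with a sea-level calibrator, x1.5 with x1.5 gives 4% at SD 0.8. The documents contain no RNA effect sizes or SDs, so the high rates depend on assumed inputs.

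Two further points have weight. B5.8.2 says alpha will be adjusted for multiple comparisons. At an illustrative 0.01, x2 with x1.5 gives 3–13% over SD 0.5 to 0.3, rather than 13–35%; this is lower but still above the nominal level. And a fold-scale interaction is false only relative to the multiplicative scale; on the additive fold scale the non-additivity is real. But delta-delta-CT is itself a multiplicative measure, so that is the natural scale on which to judge it.

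None of this supplies the missing specification. The cross-reference leads to no description, and the result of the test depends on what was left out.

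**Conclusion.** The point holds as a conditional one. The plan names fold change as the RNA measure, sends RNA to a linear time-by-phase model, and states neither calibrator nor scale. If fold changes against a common sea-level pre-exercise calibrator are the response, the interaction test can depart far from its nominal 5%. Under the assumed SDs of 0.3 to 0.8 cycles, the rate runs from 75% down to 9% for two twofold effects, and from 35% down to 5% for x2 with x1.5. Power for a true interaction can also fall sharply when altitude lowers expression and the interaction runs the other way.

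Two stronger conclusions are not supported: that the plan states this choice outright, and that the artefact follows whenever both effects are present. It needs a common calibrator, two effects of some size and moderate within-person variation.

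The outcomes are exploratory and mechanistic. The paired t-test on glucose oxidation, and with it the confirmatory aim, is untouched.

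**What to change.** Add to B5.4 and B5.8.2: *Mixed models for mRNA and microRNA are fitted to delta-CT values; contrasts and 95% CIs are back-transformed as 2^-(contrast) and reported as fold changes, and the calibrator used for display is stated.*

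This supplies the description that B5.4 refers to and keeps the phase effect and the interaction as separate results. It holds the interaction test at about 5% in every setting simulated and makes it independent of the calibrator, which then matters only for presentation.

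The cost is one sentence. Samples, assays, software and reported units stay the same.

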#### 33 Western Blotting

34 To understand potential molecular regulation of changes in substrate metabolism during exercise at SL  
35 and HA this study will examine alterations in phosphorylation and total protein content of signaling  
36 proteins associated with substrate metabolism. Following previously published methods (36), ~30 mg  
37 of muscle will be homogenized in ice-cold buffer to extract proteins for Western blotting. Protein  
38 concentration of supernatant (lysate) will be determined using 660 nm Protein Assay (ThermoFisher  
39 Scientific, Waltham, MA, USA). Phosphorylation status and total protein expression of molecular  
40 markers associated with regulating substrate metabolism, through glycolysis, TCA cycle, fatty acid  
41 oxidation, and glucose uptake. Muscle lysates will be solubilized in Laemmli buffer, with equal amounts  
42 of total protein (15 µg) separated by SDS-PAGE using precast Tris·HCl gels (Bio-Rad). Proteins will be  
43 transferred to polyvinylidene fluoride (PVDF) membranes and exposed to commercially available  
44 primary antibodies at 4°C overnight. Labeling will be performed using secondary antibody (anti-rabbit  
45 IgG conjugate with horseradish peroxidase; Cell Signaling Technology), and chemiluminescent reagent  
46 will be applied (Super Signal, West Pico Kit; Pierce Biotechnology, Rockford, IL, USA). Blots will be  
47 quantified using a phosphoimager (ChemiDoc XRS; Bio-Rad) and Image Lab software (Bio-Rad). To  
48 confirm equal protein loading per well a normalizing protein such as GAPDH or HSP90 will be  
49 assessed.  
50

#### 51 Enzyme Activity

1 Colorimetric enzyme activity assays will be conducted to assess the impact of altitude exposure on  
2 substrate energy metabolism, to include but not limited to pyruvate dehydrogenase (PDH) and citrate  
3 synthase.

4  
5 Pyruvate dehydrogenase (PDH) activity will be measured from approximately 10 mg of muscle  
6 homogenized in 100 µl of ice-cold PDH Assay Buffer (Sigma-Aldrich). Samples will be loaded into a 96  
7 well clear plate with PDH developer (Sigma-Aldrich) and incubated at 37°C for 3 min. Initial PDH  
8 activity will be read at 450 nm. Samples will continue to be incubated at 37°C and read every 5 min  
9 until the highest standard value (12.5 nmol) is met. A final absorbance measurement will be taken at  
10 450 nm. Change in absorbance will be calculated from initial and final read.

11  
12 Homogenate from muscle samples prepared for Western blotting will be used to assess citrate  
13 synthase activity, by combining 10 µl of diluted (1:10; 0.1 M Tris HCl pH 8.1) sample to 150 µl of  
14 reaction master mix (1 mL DNTB, 3 mg Acetyl CoA, and 8 mL 0.1 M Tris HCl pH 8.1). The reaction will  
15 be initiated when 10 µl of 10 mM oxaloacetate will be added to each well (37). Samples will be read at  
16 412 nm. Data will be normalized to protein content of muscle homogenate.

17  
18 Enzyme activity will be determined using a colorimetric assay analyzed on an SpectraMax® M Series  
19 Multi-Mode Microplate Reader (Molecular Devices, Sunnyvale, CA, USA).

20  
21 Any use of the data or samples outside of this defined research plan will be submitted as a protocol  
22 amendment or a new protocol.

## 23 **B5.5 Managing Data and/or Human Biological Specimens for this Research**

24  
25 All data and medical information obtained will be considered privileged and held in confidence. Study  
26 volunteers will be assigned unique subject identification (ID) numbers that will not contain any personal  
27 identifiers such as name, social security number, address, date of birth, zip code, etc. This study  
28 subject ID number will be used on all data collection instruments, to include questionnaires, data  
29 collection forms, computer records, etc. A number will be assigned as each volunteer is medically  
30 cleared for participation. A master list linking the volunteers' names and ID numbers will be kept in a  
31 separate locked file in the principal investigator's office, or kept in a computer file with password-  
32 protected access restricted to the principal investigator. When the results of the research are published  
33 or discussed in conferences, no information will be included that would reveal identity. Study samples  
34 will be processed on site at USARIEM. All samples will be stored using the subject identification  
35 number. De-identified blood and urine will be shipped on dry ice to PBRC for analysis. De-identified  
36 samples for isotopic analysis will be shipped on dry ice to UAMS (blood) and Metabolic Solutions (blood  
37 and breath). All samples will be shipped via FedEx and stores in these laboratories until analyzed.  
38 Once analyzed, there will be no remaining sample for storage.

39  
40  
41 Only personnel assigned to the research study by the principal investigator will have access to the data.  
42 Hard copy data records will be stored for a minimum of three years from the time the study is  
43 completed. Electronic data records will be maintained for a period of at least five years after the study  
44 has been completed.

## 45 **B5.6 Managing Data and/or Human Biological Specimens for Future Research**

46  
47 The master list linking subjects with their data will be destroyed when the study is closed. De-identified  
48 study samples will be stored in -80°C freezer at USARIEM in room 322 or 304 for potential future use.  
49 All samples will be de-identified and maintained indefinitely. Only personnel assigned to the research  
50 study by the principal investigator will have access to samples. The de-identified data and samples will  
51 remain under the control of the PI and may be shared with outside collaborators for future research.  
52 Any use of the samples outside of this defined protocol will be submitted as a protocol amendment or a  
53

1 new protocol.  
2

## 3 **B5.7 Devices, Drugs, Dietary Supplements, Nutritional Supplements, And Biologics**

### 4 **B5.7.1 Devices**

5  
6 **5.7.1.1 FDA-approved device being used in this research according to the approved**  
7 **labeling.** DEXA, DPX-IQ, Lunar Corporation, True Max 2400, Parvomedics, Sandy, Utah, USA,  
8 Polar Electro Inc, Oulu, Finland  
9

10  
11 **5.7.1.2 FDA-approved device being used in this research in a manner other than its**  
12 **approved labeling**

